10.4.2 Listing of Randomized Subjects not Included in the Primary Efficacy Analysis

A listing of the randomized subjects that were not included in the primary efficacy analysis will be prepared. The listing will include the reason(s) the subject was not included (did not receive study drug, had no baseline observation, and/or had no post-baseline observation within 45 days after the last dose of study drug).

10.5 Combination of Sites with Fewer than 2 Subjects per Treatment Group

When "site" is included as a factor in a statistical model, sites that do not have at least 2 subjects per treatment group for the ITT dataset will be combined within each country as follows.

1. Divide the sites into 2 groups with Group 1 including all sites that have at least 2 subjects per treatment group and Group 2 including all remaining sites. Sort each group in ascending order by total sample size and investigator number.

2. Starting at the top of the Group 2 list (i.e., the first site with the smallest sample size), combine the minimum number of sites required to achieve a pseudo-site that has at least 2 subjects per treatment group. Continue this process until all Group 2 sites have been grouped into pseudo-sites.
3. If there is a site (or sites) left after Step 2, combine this site (or sites) with the last pseudo-site that is created. For the situation where there is no previous pseudo-site exists, combine this site (or sites) with the first site on the sorted Group 1 list.

The naming of the pseudo-sites will be given by xxx99901, xxx99902, etc., where xxx is the country code.

The combined pseudo-sites will be used in all statistical models that include the "Site" as a factor. However, the original site identification will be used in all summaries of subject disposition or discontinuation by Study Site and in all data listings. In the summaries of the number and percentage of subjects contributed by each site in each treatment group for the ITT dataset, the name of pseudo-sites will also be displayed.

10.6 Handling of Missing Data for Efficacy Assessments and Sensitivity Analysis of the Primary Efficacy Endpoint

Missing Items for a Rating Scale

Unless otherwise specified, when an efficacy variable is a total score calculated from a set of individual items, the total score will be considered missing if any of the individual items are missing.

Missing Visit Data

Before conducting any imputation of missing data, patterns of missing data for the primary endpoint CDR-SB score in placebo and three ABBV-8E12 arms will be assessed. Observed mean changes from baseline in CDR-SB score will be summarized over time for different missing patterns of longitudinal data (discontinued before Week 24 assessment, discontinued after Week 24 assessment, discontinued after Week 48

assessment, discontinued after Week 48 assessment, discontinued after Week 72, completer). Number of subjects and percentage of subjects for each missing pattern will be summarized as well.

To evaluate robustness of the primary efficacy results on CDR-SB score changes from baseline, sensitivity analysis will be conducted using a multiple imputation (MI) method assuming a missing pattern that is mostly monotonic in this study and missing at random (MAR). The COVID-19 pandemic is interfering with the conduct of ongoing Study M15-566, with potential impact on treatment duration and the data collection, analysis and interpretation of clinical trial data. The probability of having missed visits and missing data due to COVID-19 infection or logistical restrictions related to the COVID-19 pandemic can be reasonably assumed to be unrelated to the unobserved values conditional on the observed data. Therefore, for the purpose of statistical analysis, it is reasonable to assume that these missing data are MAR and the MMRM analysis model that is based on MAR assumption is appropriate.

Sensitivity analysis will be conducted only if at least one ABBV-8E12 dose is statistically significant different from placebo after multiplicity adjustment for the primary endpoint in the primary efficacy analysis.

Sensitivity analysis using MI will be conducted in the following three steps:

1. Use Monte Carlo Markov Chain (MCMC) methodology from PROC MI to impute the intermittent missing data so that a monotone missing pattern can be obtained for treatment group
2. Impute missing data to create 20 complete datasets including observed CDR-SB change from baseline scores for subjects with scores for all 4 visits as well as observed and imputed change from baseline scores for subjects with missing visits using the MI method

3. Analyze each imputed dataset generated in Step 1 with the same analysis model for the primary efficacy analysis of the primary endpoint and keep analysis results for each imputed dataset
4. Combine analysis results across imputed datasets.

The MI method will be used to impute missing data at various visits overtime. The MI method will be applied separately for each ABBV-8E12 dose arm and placebo arm. Multivariate regression models will be used to impute CDR-SB missing data for different visits. To impute missing values for CDR-SB score for Visit X, variables included in the imputation model are baseline CDR-SB score, CDR-SB score before discontinuation at Visit X, investigator sites. A mean vector and variance covariance matrix based on all available cases will be used for the imputation. If the monotonic missing pattern is not satisfied, the MCMC method will be used to create monotonic missing pattern by filling missing values between visits where data are observed. Imputed CDR-SB score needs satisfy the range requirement for the scale (integer and half integer value between 0 and 18. If an imputed value is not in the range, it will be rounded down to 18 if greater than 18 or rounded up to 0 if less than 0). The MI will be implemented using PROC MI in SAS 9.4. In Step 3, PROC MIANALYZE procedure will be used to combine MMRM analysis results based on 20 imputed datasets.

10.7 Handling of Multiplicity

Pairwise comparisons between each ABBV-8E12 dose group and the placebo group will be performed using two-sided tests. A group-sequential graphical approach^{4,5} will be applied for multiplicity control for multiple comparisons due to multiple endpoints, multiple ABBV-8E12 doses and multiple interim analyses (IA) and final analysis. The overall family-wise error rate (FWER) will be controlled at the two-sided 5% level.

[figure not shown]
The primary endpoint and two ranked key secondary efficacy endpoints will be included for the FWER control in this study. These endpoints are presented in [Table 4](#). The initial alpha allocation to the primary hypotheses for three doses and alpha propagation among

hypotheses are presented in [Figure 2](#). The ranked secondary endpoints hypotheses for a dose can be tested only if the primary endpoint hypothesis is rejected for that dose. The primary endpoint hypothesis is the gatekeeper for testing the key secondary endpoints hypotheses and a higher ranked endpoint hypothesis is the gatekeeper for testing the lower ranked endpoint hypothesis for each dose. O'Brien-Fleming (OBF) p-value boundaries will be used for all endpoints' hypotheses testing at interim and final analyses. The detailed group-sequential graphical testing procedure is described below. A summary table for multiplicity adjustment will be prepared. The table will include rejection boundary for each hypothesis at each analysis, observed p-value for testing each hypothesis at each analysis.

Table 4. Hypotheses Included in the Group-sequential Graphical Procedure

Hypothesis Family	Endpoint	Comparative Hypotheses	Notation of Hypotheses
Primary family	CDR-SB score change from baseline at Week 96	ABBV-8E12 2000 mg vs. placebo	H11
		ABBV-8E12 1000 mg vs. placebo	H21
		ABBV-8E12 300 mg vs. placebo	H31
Secondary family	ADAS-Cog-14 total score change from baseline at Week 96	ABBV-8E12 2000 mg vs. placebo	H12
		ABBV-8E12 1000 mg vs. placebo	H22
		ABBV-8E12 300 mg vs. placebo	H32
	FAQ total score change from baseline at Week 96	ABBV-8E12 2000 mg vs. placebo	H13
		ABBV-8E12 1000 mg vs. placebo	H23
		ABBV-8E12 300 mg vs. placebo	H33

Figure 2. An Initial Graph for Alpha Allocation and Propagation

Note: Numbers inside each circle is the amount of alpha allocated initially for each hypothesis. Numbers in rectangle boxes on arrow lines are weights for alpha propagation among hypotheses.

The steps to perform hypotheses testing procedure is summarized below:

- Step 0: Set $I = \{H11, H21, H31, H12, H22, H32, H13, H23, H33\}$. Initial alpha allocation weights $w = (16/25, 8/25, 1/25)$ and corresponding alpha level (0.032, 0.016, 0.002) for CDR-SB change from baseline at Week 96 will be allocated to 2000 mg, 1000 mg and 300 mg doses (H11, H21, H31), respectively. Zero alpha is allocated initially to all secondary endpoints' hypotheses. Initial propagation weights (g) between hypotheses are assigned and listed in Figure 2. The p-value (two-sided) initial OBF rejection boundaries for 3 analyses (IA2, IA3, and final analyses) for the primary

endpoint are calculated using pre-allocated alpha levels with information fractions of 45%, 75% and 100% for IA2, IA3 and final analysis, respectively. The initial P-value boundaries for CDR-SB change from baseline at Week 96 are presented in [Table 5](#). Initial OBF P-value rejection boundaries for all secondary endpoints are set to be (0.0, 0.0, 0.0) because no alpha is allocated for any secondary endpoint hypothesis.

Table 5. Initial OBF P-Value Boundaries for CDR-SB Change from Baseline at Week 96

	IA2	IA3	Final
ABBV-8E12 2000 mg (H11): alpha = 0.032			
OBF two-sided p-value boundary	0.00106	0.01126	0.02816
Cumulative alpha spending	0.00106	0.01166	0.032
ABBV-8E12 1000 mg (H21): alpha = 0.016			
OBF two-sided p-value boundary	0.00026	0.00472	0.01438
Cumulative alpha spending	0.00026	0.00482	0.016
ABBV-8E12 300 mg (H31): alpha = 0.002			
OBF two-sided p-value boundary	0.00001	0.00034	0.00188
Cumulative alpha spending	0.00001	0.00034	0.002

- Stage k (k = IA2, IA3, Final):

Step 1: obtain Week 96 p-values for the primary and key secondary endpoints.

Step 2: compare p-values in step 1 against the boundaries for analysis at Stage k. If one or more hypotheses are rejected, go to Step 3. Otherwise, go to Step 5.

Step 3: update the graph ([Figure 2](#)) using the method proposed by Bretz et al. (2009).⁶ If none of hypothesis is rejected, then go to Step 5 without updating the boundaries and [Figure 2](#). The following are steps to update the graph with updated alpha allocation weights for each hypothesis and alpha propagation weights among hypotheses:

- $I \rightarrow I \setminus \{i\}$, i.e., update Set I after the i^{th} hypothesis is rejected and excluded from Set I .
- $w_j \rightarrow w_j + w_i g_{ij}, j \in I; 0$, otherwise. w_j is updated alpha allocation weight for hypothesis j , w_i is alpha allocation weight for hypothesis i , g_{ij} is the alpha propagation weight from hypotheses i to j .
- $g_{ih} = (g_{ih} + g_{ji} g_{ih}) / (1 - g_{ji} g_{ij}), j, h \in I, j \neq h, g_{ji} g_{ij} < 1; 0$, otherwise. g_{ji} is the alpha propagation weight from hypotheses j to i , g_{ih} is the alpha propagation weight from hypotheses i to h .

Step 4: calculate new OBF p-value boundaries for all endpoints with updated significant levels obtained in Step 3 and go to Step 2.

Step 5: go to next stage ($k + 1$) and go to Step 1 or stop the testing.

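### SAP 10.7 prints the propagation-weight update with the wrong subscripts, so as written the graph is not properly defined from the second rejection on

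*SAP*

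**What the plan says.** SAP 10.7 promises that "The overall family-wise error rate (FWER) will be controlled at the two-sided 5% level". The primary hypotheses for 2000, 1000 and 300 mg (H11, H21, H31) start with "corresponding alpha level (0.032, 0.016, 0.002"). For ADAS-Cog-14 (H12, H22, H32) and FAQ (H13, H23, H33) it says: "Zero alpha is allocated initially to all secondary endpoints' hypotheses". The initial propagation weights "are assigned and listed in Figure 2"; that figure is not shown in the text available here.

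Step 3 cites a published graphical method (SAP reference 6) and then sets out the operations: "The following are steps to update the graph with updated alpha allocation weights for each hypothesis and alpha propagation weights among hypotheses". There are three:

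1. Remove the rejected hypothesis i from Set I.
2. Set `w_j -> w_j + w_i g_ij` for j in I.
3. Set `g_ih = (g_ih + g_ji g_ih)/(1 - g_ji g_ij)` for j, h in I, j not equal to h, `g_ji g_ij < 1`, and 0 otherwise.

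The text defines g_ij in item 2, and g_ji and g_ih in item 3. Each "is the alpha propagation weight from hypotheses" its first index to its second. The symbol g_jh does not appear.

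Step 4 then says to "calculate new OBF p-value boundaries for all endpoints with updated significant levels obtained in Step 3 and go to Step 2". Protocol 8.1.3 leaves the detailed testing procedure to the SAP and the DMC Charter, so this is operative text.

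**The concern.** Once i has been rejected, what has to be updated is the weight from each remaining hypothesis j to each other remaining hypothesis h. The printed rule runs over pairs (j, h) but assigns to g_ih, which has no j in it and belongs to a node already removed. An analyst who follows the page cannot obtain the weights that the cited method would give. At stake are the significance levels at later rejections, which in this design means mostly the key secondary endpoints and any dose tested after two others have succeeded.

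**Working it through.** **The plan's own figures.** The initial levels add up: 0.032 + 0.016 + 0.002 = 0.050. Table 5 uses "information fractions of 45%, 75% and 100% for IA2, IA3 and final analysis, respectively". Classical O'Brien-Fleming boundaries c/sqrt(t) at t = 0.45, 0.75, 1 with c = 2.195 give two-sided p-values of 0.00107, 0.01125 and 0.02815 for H11, against 0.00106, 0.01126 and 0.02816 printed. The other two rows also agree to within 0.00001. The starting point is sound.

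**Assumed graphs.** Figure 2 is not shown, so every weight below is an assumption. In both graphs each primary passes a share a to its own ADAS-Cog-14, ADAS-Cog-14 passes everything to FAQ at the same dose, and FAQ passes its alpha back to other doses' primaries. In the symmetric graph a primary splits 1 - a equally between the other two doses. In the cyclic graph it passes 1 - a along 2000 to 1000 to 300 to 2000 mg. I used a = 0.25, 0.5 and 0.75.

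**The printed rule has no unique value.** Symmetric graph, a = 0.5, i = H11, h = H12, so g_ih = 0.5:
- j = H21, with g_ji = g_ij = 0.25: (0.5 + 0.25 x 0.5)/(1 - 0.0625) = 0.667
- j = H22, with g_ji = g_ij = 0: 0.50
- j = H23, with g_ji = 0.5 and g_ij = 0: (0.5 + 0.25)/1 = 0.75

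One weight receives three values.

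**Reject H11, then H21 (symmetric, a = 0.5).** The first rejection uses only the initial weights and the correct w_j step:
- H12 = 0.032 x 0.5 = 0.016
- H21 = 0.016 + 0.032 x 0.25 = 0.024
- H31 = 0.002 + 0.008 = 0.010
- Total 0.050, right under any reading.

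The second rejection passes on H21's 0.024.

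| Reading | H21 to H22 | H21 to H31 | H21 to H12 | H22 | H31 | H12 | Total |
|---|---|---|---|---|---|---|---|
| (a) Standard update | 0.5/0.9375 = 0.533 | (0.25 + 0.0625)/0.9375 = 0.333 | 0.125/0.9375 = 0.133 | 0.0128 | 0.0180 | 0.0192 | 0.0500 |
| (b) Literal: remaining weights unchanged | 0.50 | 0.25 | 0 | 0.0120 | 0.0160 | 0.0160 | 0.0440 |
| (c) Printed right side assigned to g_jh | 0 | 0.333 | 0.667 | 0 | 0.0180 | 0.0320 | 0.0500 |

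Under (b), 0.024 x 0.25 = 0.006 goes to the removed H11 and is lost. Under (c), H22 receives nothing although its gatekeeper H21 has just been rejected.

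**Range for (b).** Totals after H11 then H21 on the symmetric graph are 0.0395, 0.0440 and 0.0475 for a = 0.25, 0.5 and 0.75. On the cyclic graph that sequence loses nothing, but the total falls to 0.026, 0.041 and 0.048 once H31 is also rejected.

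**Why (b) cannot inflate.** The correct update adds the non-negative term g_ji g_ih and divides by a number no greater than 1, so the correct g_jh is never smaller than the unchanged one. Levels under (b) therefore never exceed the correct levels, and any rejection under (b) would also occur under the valid procedure.

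**Why (c) can exceed 0.05.** If i's outgoing weights sum to 1, row j under (c) sums to `(1 - g_ij)(1 + g_ji)/(1 - g_ji g_ij) = 1 + (g_ji - g_ij)/(1 - g_ji g_ij)`, which is above 1 whenever g_ji > g_ij. Cyclic graph, a = 0.5, H21 then H11:
- After H21: H22 = 0.008, H31 = 0.002 + 0.008 = 0.010, H11 still 0.032.
- H11's new weights are 0.5 x 1.5 = 0.75 to H22 and 0.75 to H31.
- After H11: H22 = 0.008 + 0.024 = 0.032 and H31 = 0.010 + 0.024 = 0.034, total 0.066.

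For a = 0.25 and 0.75 the totals are 0.074 and 0.058. On the symmetric graph no sequence tried under (c) exceeded 0.05. The standard update kept 0.0500 in every sequence tried on both graphs.

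**The case against.** The case for leaving this as an editorial note has real force.

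- **The method is named.** Step 3 cites the published procedure, and validated software for it would give the right answer. The printed line cannot be run as it stands, so a careful programmer would go to the source. This stands and limits the practical risk. It also means that the SAP's printed steps and its cited method disagree, so an independent programmer working from the SAP could not reproduce the result.
- **The text was read from a PDF.** A subscript misread is possible. The definitions given (g_ij, g_ji, g_ih) are exactly the other weights that the correct formula needs, and the condition on j and h suits g_jh. Against this, two positions would have to be misread while g_ij and g_ji in the same line came through intact, and g_jh would still lack a definition. Unlikely, not excluded.
- **Stronger readings do not hold.** A reader might infer that every level after the first rejection is wrong. It is not: levels come from the w_j step, which is correct and at that point uses the initial weights. A reader might infer that familywise error is inflated. The literal reading is conservative, and inflation needs both a reading that the SAP does not state and particular Figure 2 weights. A reader might infer that the endpoint ranking is broken. SAP 10.7 states the gates separately in words: the primary gates the secondaries at each dose, and the higher-ranked secondary gates the lower.

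**Conclusion.** The printed update is wrong as it stands in the text. The left side and the first numerator term should run from j to h; the last numerator term, g_ih, is correct. The error can matter only from the second rejection on.

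Its direction depends on how the line is implemented. Leaving the remaining weights unchanged costs alpha and power and cannot raise familywise error above 5%. Assigning the printed right side to g_jh can send alpha to the wrong hypothesis, or bring the remaining levels to a total above 0.05, at which point the Bonferroni argument behind the 5% claim no longer applies. The documents do not show that either would happen in this trial. All totals other than the initial 0.050 rest on assumed graphs and illustrate direction, not the trial's own loss or excess. The conclusion also assumes that the subscripts were read correctly from the page. A pre-specified confirmatory algorithm should be executable as written, so this should be corrected.

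**What to change.** First check the subscripts in this line on the original SAP page. If they stand as read here, then:

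1. Print the update as `g_jh -> (g_jh + g_ji g_ih)/(1 - g_ji g_ij)` for j, h in I, j not equal to h, `g_ji g_ij < 1`; 0 otherwise.
2. Define g_jh as the propagation weight from hypothesis j to hypothesis h.
3. Add a programming check that each row of updated weights sums to at most 1 after every rejection.

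The cost is one corrected line, one definition and a routine check. The design, initial alpha allocation, Table 5 boundaries and analyses do not change. If the DMC Charter or the interim analysis programs carry the same line, correct it there too.

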10.8 Efficacy Subgroup Analysis

To examine whether gender, age group (< 65 vs \geq 65 years old), APOE4 carrier status (carrier vs non-carrier), baseline AD medication use (use vs no use. AD medications are defined in Section 7.1), baseline amyloid PET level (baseline centiloid value < median vs \geq median), and geographical region [North America (US and Canada) vs other countries] have an impact on response to treatment, subgroup analyses on CDR-SB change score will be conducted using an ANCOVA model with the terms of treatment, subgroup variable, site (site is nested within a region for geographical region subgroup analysis), the treatment-by-subgroup variable interaction, and baseline score as a covariate. The hypothesis that consistent response to treatment across strata of a subgroup variable will be tested at the significance level of 0.100 by examining the P value of the treatment-by-subgroup interaction term in the ANCOVA model specified above. The statistical comparison of each ABBV-8E12 dose group with placebo within each subgroup stratum will be performed when the statistical significance of the treatment-by-subgroup interaction term is achieved at 0.100 level. The subgroup analysis will be conducted on the ITT dataset.

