8.1.4 Subgroup Analysis of CDR-SB Score

To examine whether gender, age group, study site, country/geographic region or other baseline variables have an impact on response to treatment, subgroup analyses on CDR-SB score will be conducted on change from baseline to last observations up to Week 96. Subgroup analyses will be performed using an ANCOVA model with the terms of treatment, site, subgroup variable, the treatment-by-subgroup variable interaction, and baseline score as a covariate. The subgroup analysis for country/region will be performed using the same model but with the study site nested within geographic region. The hypothesis that consistent response to treatment across strata of a subgroup variable will be tested at the significance level of 0.100 by examining the P value of the treatment-by-subgroup interaction term in the ANCOVA model specified above. The statistical comparison of each ABBV-8E12 dose group with placebo within each stratum will be performed when the statistical significance of the treatment-by-subgroup interaction term is achieved at 0.100 level. The subgroup analysis will be conducted in the ITT data set.

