7.1 Demographic and Baseline Characteristics

The following demographic and baseline characteristics will be summarized for each treatment group, for the combination of all ABBV-8E12 dose groups ("ABBV-8E12 Overall") and for the combination of all treatment groups ("Total Subjects") for the safety dataset.

- Gender (male/female)
- Race (white, black, American Indian/Alaska native, Native Hawaiian or other Pacific Islander, Asian, Other, Multi-Race)
- Education (high school or above, lower than high school)
- Ethnicity (Hispanic or Latino)
- Age (years)
- Age group (< 65, ≥ 65)
- Weight for all subjects (kg)
- Weight for all male subjects (kg)
- Weight for all female subjects (kg)
- Height (cm)
- Body mass index (BMI, kg/m²)
- Body mass index category (BMI, kg/m²) (< 25, ≥ 25)
- APOE allele status (ε2ε2, ε2ε3, ε2ε4, ε3ε3, ε3ε4, ε4ε4)

- Baseline AD medication use: AChEI (donepezil, rivastigmine, galantamine) and memantine

Alcohol and tobacco uses will be summarized for each treatment group, ABBV-8E12 Overall and Total Subjects for the safety dataset. For alcohol use, the number and percentage of subjects who are drinkers, ex-drinkers and non-drinkers (defined as those who have never been a drinker) will be presented. For the tobacco use, the number and percentage of users, ex-users and non-users (defined as those who have never been a user) will be presented. A subject reporting multiple use categories for the different types of tobacco (cigarette, pipe, cigar and chewing tobacco) will be counted in the tobacco user category.

The following baseline efficacy variables will be summarized for each treatment group, ABBV-8E12 Overall and Total Subjects for the ITT dataset.

- CDR-SB score
- ADAS-Cog-14 total score and subscale scores
- FAQ total score
- UPSA-Brief score
- ADCS-MCI-ADL-24 total score
- RBANS total scale score and subtest scores
- MMSE total score
- NPI total score
- ADCOMS score

ADCOMS score is a composite score which is a weighted linear combination of the remaining individual scale items from ADAS-cog, MMSE, and CDR-SB scales. The weights for items are listed below.³

Scale	Item name	Weights
ADAS-cog	Delayed word recall	0.008
	Orientation	0.017
	Word recognition	0.004
	Word finding difficulty	0.016
MMSE	Orientation time	0.042
	Drawing	0.038
CDR-SB	Personal care	0.054
	Community affairs	0.109
	Home and hobbies	0.089
	Judgement and problem solving	0.069
	Memory	0.059
	Orientation	0.078

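### SAP 10.8 tests whether the CDR-SB effect depends on amyloid or age only through two-level cuts; a continuous interaction should be added alongside them

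*SAP*

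**What the plan says.** SAP 10.8 lists six subgroup variables for the CDR-SB change score. Two of them are continuous by nature and are cut in two: "age group (< 65 vs \geq 65 years old" and "baseline amyloid PET level (baseline centiloid value < median vs \geq median". Each goes into an ANCOVA with treatment, the subgroup variable, site, their treatment interaction and baseline score. The consistency hypothesis "will be tested at the significance level of 0.100 by examining the P value" of the interaction term. The dose-placebo comparisons within a stratum "will be performed when the statistical significance of the treatment-by-subgroup interaction term is achieved at 0.100 level", so the interaction test is also a gate.

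Protocol 8.1.4 has the same model and speaks only of an age group and other baseline variables: "To examine whether gender, age group, study site, country/geographic region or other baseline variables have an impact on response to treatment". It gives no age cut and does not name amyloid. SAP 7.1 lists age in years as well as "Age group (< 65, ≥ 65". SAP 14.0 records that the centiloid criterion was updated in version 3.0, without a reason.

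**The concern.** A two-level factor treats everyone in the same stratum as alike. If the treatment effect rises or falls gradually with amyloid burden or age, the differences within each stratum carry information about that gradient, and the cut discards it. The result also depends on where the cut falls. The median is fixed by the sample and has no stated biological meaning, and the age cut may leave unequal strata.

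These are the only planned analyses of whether the CDR-SB effect depends on amyloid or age. Because the interaction test gates the within-stratum comparisons, a missed gradient also means that no formal dose-placebo comparison by amyloid level or age follows.

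**Working it through.** **Inputs from the documents.** 100 per arm, 25% without post-baseline data, planning effects 0.45/0.45/0.28 SD, one-sided 2.5% with Bonferroni (SAP 4.3); interaction level 0.100 (SAP 10.8); age 55–85 and a positive amyloid PET scan (Protocol 5.2.1). Four arms and two strata give a 3-df interaction. Evaluable per arm: 100 × 0.75 = 75.

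**The plan's own figure.** Simulating three z tests that share a placebo arm, with 75 per arm and each at one-sided 0.025/3, gives 80.6% power for at least one significant dose. This agrees with the stated figure of about 80%. The documents state no power for any subgroup interaction.

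**Information kept by a cut, if the interaction is linear.** This is the squared correlation between the moderator X and the indicator X ≥ c. With share p below the cut:
- Normal X: φ(z_p)²/[p(1−p)]. At p = 0.5 this is 2/π = 0.637, a loss of 36%.
- Uniform X: 3p(1−p). At p = 0.5 this is 0.75, a loss of 25%.

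*Centiloid at the median (distribution assumed):*

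| Shape | Loss |
|---|---|
| Uniform | 25% |
| Bimodal mixture | 25% |
| Normal truncated below at 20–25 centiloid | 34–36% |
| Normal | 36% |
| Lognormal, log-SD 0.25 to 0.75 | 40–61% |

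*Age at 65 (share under 65 assumed):*

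| Share under 65 | Normal | Uniform |
|---|---|---|
| 50% | 36% | 25% |
| one third (flat over 55–85) | 40% | 33% |
| 20% | 51% | 52% |
| 10% | 66% | 73% |

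Normals truncated to 55–85 with assumed mean 67–73 and SD 6–10 lose 37–66%. Roughly 25–65% covers these cases, except a flat distribution with very few under 65.

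**Power of the 3-df test at 0.100.** For a standard normal moderator the two median halves differ in mean by 2√(2/π) = 1.596. A difference in effect of 0.45/0.45/0.28 SD between halves therefore needs slopes of 0.45/1.596 = 0.282 (twice) and 0.28/1.596 = 0.175 per SD. With placebo at 0, the mean slope is 0.185 and the squared deviations sum to 0.0531. Noncentrality is n × information kept × this sum, with 3 and 292 df:
- Continuous: 75 × 1 × 0.0531 = 3.98, power 48%.
- Median split: 75 × 0.637 × 0.0531 = 2.54, power 34%.
- Cut with 20% below: 75 × 0.49 × 0.0531 = 1.95, power 29%.

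Simulated F tests gave 47%, 33% and 28%. With steeper slopes of 0.45/0.45/0.28 per SD the calculated figures are 85%, 67% and 56%.

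**If the truth is a step.** Let the effect jump by 0.45/0.45/0.28 SD exactly at the median. The squared deviations of these jumps sum to 0.1353 and the indicator has variance 0.25. The split has noncentrality 75 × 0.25 × 0.1353 = 2.54 (34% power). The linear term has 0.637 × 2.54 = 1.62 (26%).

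For a step at percentile p < 0.5 of a normal moderator, the median split keeps p/(1−p) of the information and the linear term keeps φ(z_p)²/[p(1−p)]. At the 45th percentile this is 82% against 63%, and at the 40th 67% against 62%. The two are about equal near the 38th and, by symmetry, the 62nd.

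**The case against.** The best case for the plan has five parts.

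- **No single loss figure is established.** A reader might infer that the cuts discard at least 36% of the information. The documents do not support that as a floor. It is the value for a normal moderator with a linear gradient cut at its median; both variables are truncated by the entry criteria, and neither distribution is given. This stands, so the loss is given as a range.
- **The split can win.** A reader might infer that a cut is better only for a step at exactly that value. That is wrong: for a normal moderator the median split is better for any step from about the 38th to the 62nd percentile. It can also be better for a steep smooth change centred at the median. This stands.
- **A small stratum under 65 is not documented.** A flat distribution over 55–85 would put one third there. This stands.
- **The gain is modest and the analysis supportive.** The assumed gradient is large, since the halves differ by the whole planning effect, yet the continuous test reaches only about 48%. The subgroup tests lie outside the error-controlled family of SAP 10.7. This stands, and it limits the importance of the point.
- **Centiloid may not be comparable for everyone.** Protocol 5.3.1.1 accepts historical amyloid-positive scans, and the documents do not say that these yield a comparable value. A median split also needs a numeric centiloid, so this affects both analyses.

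None of this supplies a reason for using the cuts alone. SAP 13.0 already fits CDR-SB models with a continuous covariate and its interaction with treatment, also judged at 0.100. The change of criterion noted in SAP 14.0 is not in itself evidence of a flaw.

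**Conclusion.** The point holds as a minor improvement. Amyloid and age enter the CDR-SB interaction tests only as two-level factors, with no reason given and no continuous analysis planned. For a roughly linear change, the cost is about a quarter to a third of the interaction information at the median split (more if skewed) and roughly 25–65% at age 65. In the worked case this is about 48% power against about 34%. The figures rest on 75 evaluable per arm, an assumed normal moderator for power, and an assumed gradient; the documents give none of the distributions needed to narrow them. If the effect changes as a step near the median, the split is the better test. The two analyses therefore complement each other, and the documents do not support replacing one with the other. The primary analysis is untouched.

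**What to change.** In SAP 10.8, for centiloid and age, add a pre-specified model of CDR-SB change with treatment, site, baseline CDR-SB, the centred continuous moderator and the treatment-by-moderator interaction. Check linearity with a quadratic term or spline. Report each dose-placebo difference with its 95% CI at the 25th, 50th and 75th percentiles of the moderator, whatever the interaction p-value.

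Keep the existing categorical analyses and their 0.100 gate alongside this. Reducing them to descriptive tables would remove the within-stratum comparisons that SAP 10.8 plans.

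The cost is SAP wording and one extra model per variable, with no new data collection planned. The downsides are the linearity assumption and one further unadjusted test per variable.
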